## 2. Schedule of Activities

Table JAHL.1. I4V-MC-JAHL Schedule of Activities

	Screening	Double-Blind, Placebo-Controlled							Post-treatment Follow-Up
		Period 1		Period 2					
Visit Number	1	2	3	4	5	6	7	8	801 a
Weeks from Randomization		0	1	2	4	8	12	16 or ET	
Days from Randomization		0	7	14	28	56	84	112	
Visit tolerance interval (days)	-8 to -35		±2	±2	±2	±4	±4	±4	28 ± 4 after last dose
Procedure									
Inclusion and exclusion review	X	X							
Informed consent	X								
Clinical Assessments									
Demographics	X								
Medical History	X								
Substance Use (alcohol, tobacco use)	X								
Previous and current AD treatments	X								
Weight	X	X			X	X	X	X	X
Height		X							
Vital signs (BP and Pulse)	X	X	X	X	X	X	X	X	X
Physical examination	X								
Symptom-directed physical exam b		X	X	X	X	X	X	X	X
12-lead ECG (single)	X								
Chest x-ray c (posterior-anterior view)	X								
TB test d	X								
Read PPD if applicable (48–72 hours post PPD)		X e							
Pre-existing Conditions	X								
Adverse Events		X	X	X	X	X	X	X	X
Concomitant Medication	X	X	X	X	X	X	X	X	X
Actigraphy devices dispensed	X	X	X	X					
Actigraphy devices returned f		X	X	X	X				

	Screening	Double-Blind, Placebo-Controlled							Post-treatment Follow-Up
		Period 1							Period 3
Visit Number	1	2	3	4	5	6	7	8	801 a
Weeks from Randomization		0	1	2	4	8	12	16 or ET	
Days from Randomization		0	7	14	28	56	84	112	
Visit tolerance interval (days)	-8 to -35		±2	±2	±2	±4	±4	±4	28 ± 4 after last dose
ePRO (patient diary) dispensed	X	X	X	X	X	X	X	X g	
ePRO (patient diary) returned f		X	X	X	X	X	X	X	X g
Randomization	X								
IWRS	X	X	X	X	X	X	X	X	X
IP dispensed		X	X	X	X	X	X		
IP returned and compliance assessed			X	X	X	X	X	X	
Dispense rescue TCS h			X	X	X	X	X	X	
Weigh (tube with cap) and record returned rescue TCS h				X	X	X	X	X	X
Scales									
IGA	X	X	X	X	X	X	X	X	X
EASI	X	X	X	X	X	X	X	X	X
SCORAD	X	X	X	X	X	X	X	X	X
Health Outcome Measures and Other Questionnaires i									
POEM	X	X	X	X	X	X	X	X	X
DLQI	X	X	X	X	X	X		X	X
HADS	X	X		X	X	X		X	
EQ-5D-5L		X	X	X	X	X	X	X	X
WPAI-AD		X	X	X	X	X	X	X	X
Itch NRS	X	X	X	X	X	X	X	X	X
Skin Pain NRS	X	X	X	X	X	X	X	X	X
ADSS	X	X	X	X	X	X	X	X	X
PGI-S-AD	X	X	X	X	X	X	X	X	X
C-SSRS j /Self-Harm Supplement Form	X	X	X	X	X	X	X	X	X
Self-Harm Follow-up Form k	X	X	X	X	X	X	X	X	X

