### **5.1.3. Period 3: Post-Treatment Follow-Up**

[figure not shown]
Patients who complete the study through Visit 8 (Week 16) and do not enter the long-term extension study will have a post-treatment follow-up visit (Visit 801) approximately 28 days after the last dose of investigational product.

Patients who have received at least 1 dose of investigational product and discontinue early from the study must have an ETV, and return for the post-treatment safety follow-up visit (Visit 801) approximately 28 days after the last dose of investigational product.

Patients who have discontinued investigational product but remain in the study for more than 28 days without investigational product will have an ETV if they chose to discontinue early; however, a separate follow-up visit (V801) is not required.

Patients should not initiate new systemic AD treatment during this period. However, if patients or investigators must initiate treatment, patients should complete an unscheduled visit prior to the first dose of the new therapy.

Figure JAHL.1 illustrates the study design. The 4 dosing regimens are described in Section 7.1. The blinding procedure is described in Section 7.3.

Abbreviations: AD = atopic dermatitis; eGFR = estimated glomerular filtration rate; PPD = purified protein derivative; QD = once daily; V = visit; W = week.

a Applicable to patients taking topical treatments (excluding emollients) or systemic treatments for AD at the time of screening.

b For patients randomized to the 4-mg QD dose who have renal impairment (defined as eGFR <60 mL/min/1.73 m^2), the baricitinib dose will be 2-mg QD.

c Patients for whom PPD skin test for the evaluation of tuberculosis infection was performed at V1 must return and PPD test must be read 48-72 hours after Visit 1 (post-PPD).

d Occurs approximately 28 days after the last dose of IP. Not required for those patients entering the long-term extension study JAHN.

Figure JAHL.1.

Illustration of study design for Clinical Protocol I4V-MC-JAHL.

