6.14. Safety Analyses

The general methods used to summarize safety data, including the definition of baseline value are described in Section 6.2.

Safety analyses will include data before and after rescue, unless otherwise stated, and patients will be analyzed according to the investigational product to which they were randomized at Visit 2. A sensitivity approach to the safety analyses will use data censored at last dose of the study drug for patients rescued to systemic therapy. These analyses will be conducted for treatment-emergent adverse events (TEAEs), serious adverse events (SAEs), AEs leading to permanent study drug discontinuation and special topics excluding deaths and malignancies. Additional analyses may be conducted using data after rescue to systemic therapy for some safety topics such as systemic TEAEs, and SAEs. Safety analyses will take place using the safety population defined in Section 6.2.1.

Safety topics that will be addressed include the following: AEs, clinical laboratory evaluations, vital signs and physical characteristics, Columbia Suicide Severity Rating Scale (C-SSRS), the Self-Harm Supplement Form, safety in special groups and circumstances, including adverse events of special interest (AESI) (see Section 6.14.5), and investigational product interruptions.

Unless otherwise specified, by-visit summaries will include planned on-treatment visits. For tables that summarize events (such as AEs, categorical lab abnormalities, shift to maximum value), post-last dose follow-up data will be included. Follow-up data is defined as all data occurring up to 30 days (planned maximum follow-up time) after last dose of treatment including rescue, regardless of study period. Listings will include all safety data.

For selected safety assessments other than events, descriptive statistics may be presented for the last measure observed during post-treatment follow-up (up to 30 days after the last dose of treatment including rescue, regardless of study period).

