6.14.1. Extent of Exposure

Duration of exposure (in days) will be calculated as follows:

- Duration of exposure to investigational product (including exposure after the initiation of rescue therapy): *date of last dose of study drug including rescue – date of first dose of study drug + 1.*

Last dose of study drug including rescue is calculated as last date on study drug. For patients discontinuing study drug or study due to the reason ‘Lost to Follow-up’, the duration of exposure is calculated as *date of to second last visit - date of first dose of study drug + 1.*

Total patient-years (PY) of exposure to study drug will be reported for each treatment group for overall duration of exposure. Descriptive statistics will be provided for patient-days of exposure and the frequency of patients falling into different exposure ranges in addition to cumulative exposures will be summarized.

Exposure ranges will be summarized as follows:

- ≥ 28 days, ≥ 56 days, ≥ 84 days, and ≥ 112 days
- >0 to <28 days, ≥ 28 days to <56 days, ≥ 56 days to <84 days, ≥ 84 days to <112 days, and ≥ 112 days

Overall exposure for a treatment group will be summarized in total PY which is calculated according to the following formula:

- $Exposure\ in\ PYE = sum\ of\ duration\ of\ exposure\ in\ days\ / 365.25$

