6.14.2. Adverse Events

Adverse events are recorded in the eCRFs. Each AE will be coded to system organ class (SOC) and preferred term (PT) using the Medical Dictionary for Regulatory Activities (MedDRA) version that is current at the time of database lock. Severity of AEs is recorded as mild, moderate, or severe.

A TEAE is defined as an event that either first occurred or worsened in severity after the first dose of study treatment and on or prior to the last visit date during the analysis period. The analysis period is defined as the treatment period plus 30 days off-drug follow-up time.

Adverse events are classified based upon the MedDRA PT. The MedDRA Lowest Level Term (LLT) will be used in defining which events are treatment-emergent. The maximum severity for each LLT during the baseline period up to first dose of the study medication will be used as baseline. If an event with missing severity is preexisting during the baseline period, and persists during the treatment period, then the baseline severity will be considered mild for determining treatment-emergence (that is, the event is treatment-emergent if the severity is moderate or severe postbaseline and not treatment-emergent if the severity is mild postbaseline). If an event occurring postbaseline has a missing severity, then the event is considered treatment-emergent unless the baseline is severe, in which case the event is not treatment-emergent. The day and time for events where onset is on the day of the first dose of study treatment will both be used to distinguish between pretreatment and posttreatment to derive treatment-emergence. Should there be insufficient data for AE start date to make this comparison (for example, the AE start year is the same as the treatment start year, but the AE start month and day are missing), the AE will be considered treatment-emergent.

In general, summaries will include the number of patients in the safety population (N), frequency of patients experiencing the event (n), and relative frequency (that is, percentage; $n/N*100$). For any events that are gender-specific based on the displayed PT, the denominator used to compute the percentage will only include patients from the appropriate gender.

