6.14.3. Clinical Laboratory Evaluation

For the categorical laboratory analyses (shift and treatment emergent), the analysis period is defined as the treatment period plus 30 days off-drug follow-up time. The analysis period for the continuous laboratory analyses (e.g., change from baseline) is defined as the treatment period excluding off-drug follow-up time.

All laboratory tests will be presented using the International Système (SI) and US conventional (CN) units. The performing central laboratory reference ranges will be used to define the low and high limits. Key results pertaining to the 4 key hepatic laboratory assessments (alanine aminotransferase [ALT], aspartate aminotransferase [AST], total bilirubin, and alkaline phosphatase [ALP]) will be included as a separate analysis to address the risk of liver injury as a special safety topic (see Section 6.14.5.1).

There is one special circumstance for laboratory values to be derived based on regularly scheduled, protocol-specified analytes. The low-density lipoprotein/high-density lipoprotein (LDL/HDL) ratio will be derived as the ratio of LDL cholesterol to HDL cholesterol. There are no central lab reference ranges for the LDL/HDL ratio.

The following will be conducted for the laboratory analytes collected quantitatively:

- Box plots: Values at each visit (starting at randomization) and change from last baseline to each visit and to last postbaseline measure will be displayed in box plots for patients who have both a baseline and at least 1 postbaseline visit. The last non-missing observation in the treatment period will be used as the last observation. Individual measurements outside of reference limits will also be displayed using distinct symbols overlaying the box plot. Original-scale data will be used for the display but for some analytes (for example, immunoglobulins) a logarithmic scale will be used to aid in viewing the measures of central tendency and dispersion. Unplanned measurements will be excluded. Descriptive summary statistics will be included below the box plot along with p-values resulting from between treatment comparison in change from last baseline to last observation. An ANCOVA model with explanatory term for treatment and the baseline value as a covariate will be used. These box plots will be used to evaluate trends over time and to assess a potential impact of outliers on central tendency summaries.

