6.14.4. Vital Signs and Other Physical Findings

For the treatment-emergent categorical analyses (shift and treatment emergent), the analysis period is defined as the treatment period plus 30 days off-drug follow-up time. The analysis period for the continuous analyses (e.g., change from baseline) is defined as the treatment period excluding off-drug follow-up time.

Vital signs and physical characteristics include systolic blood pressure (SBP), diastolic blood pressure (DBP), pulse, weight, and BMI. Original-scale data will be analyzed. When these parameters are analyzed as continuous numerical variables, unplanned measurements will be excluded. When these parameters are analyzed as categorical outcomes and/or treatment-emergent abnormalities, planned and unplanned measurements will be included.

The planned analyses described for the laboratory analytes in Section 6.14.3 will be used to analyze the vital signs and physical characteristics.

Table JAHL.6.8 defines the low and high baseline values as well as the criteria used to define treatment-emergence based on post-baseline values. The blood pressure and pulse rate criteria are consistent with the document *Selected Reference Limits for Pulse/Heart Rate, Arterial Blood Pressure (Including Orthostasis), and Electrocardiogram Numerical Parameters for Use in Analyses of Phase 2-4 Clinical Trials Version 1.3* approved on April 29, 2015 as recommended by the Lilly Cardiovascular Safety Advisory Committee (CVSAC).

Table JAHL.6.8. Categorical Criteria for Abnormal Treatment-Emergent Blood Pressure and Pulse Measurement, and Categorical Criteria for Weight Changes for Adults

Parameter (Units of Measure)	Low	High
Systolic Blood Pressure (mm Hg)	≤ 90 (low limit) and decrease from lowest value during baseline ≥ 20 if > 90 at each baseline visit	≥ 140 (high limit) and increase from highest value during baseline ≥ 20 if < 140 at each baseline visit
Diastolic Blood Pressure (mm Hg)	≤ 50 (low limit) and decrease from lowest value during baseline ≥ 10 if > 50 at each baseline visit	≥ 90 (high limit) and increase from highest value during baseline ≥ 10 if < 90 at each baseline visit
Pulse (beats per minute)	< 50 (low limit) and decrease from lowest value during baseline ≥ 15 if ≥ 50 at each baseline visit	> 100 (high limit) and increase from highest value during baseline ≥ 15 if ≤ 100 at each baseline visit

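### The SAP's 30-day off-drug cut-off, which it calls the planned maximum, is 2 days shorter than the protocol's Visit 801 window (28 + 4 = 32 days after last dose)

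*SAP*

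**What the plan says.** **SAP.** Section 6.14 brings data after the last dose into tables that summarize events (adverse events, categorical laboratory abnormalities, shifts to maximum), up to a limit: "Follow-up data is defined as all data occurring up to 30 days (planned maximum follow-up time) after last dose of treatment". It uses the same 30 days again for descriptive statistics on the last follow-up measurement. The limit recurs in three subsections:

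- 6.14.2, for TEAEs: "The analysis period is defined as the treatment period plus 30 days off-drug follow-up time". The event must also begin "on or prior to the last visit date during the analysis period".
- 6.14.3: "For the categorical laboratory analyses (shift and treatment emergent), the analysis period is defined as the treatment period plus 30 days off-drug follow-up time".
- 6.14.4, for categorical vital signs and physical characteristics: "the analysis period is defined as the treatment period plus 30 days off-drug follow-up time".

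The clock starts at the end of study drug. SAP 6.14.1 states: "Last dose of study drug including rescue is calculated as last date on study drug". On that definition, continued topical rescue does not lengthen the window.

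**Protocol.** The Schedule of Activities (Section 2) gives the timing of Visit 801 as "28 ± 4 after last dose". Section 5.1.3 says that completers who do not enter the extension "will have a post-treatment follow-up visit (Visit 801) approximately 28 days after the last dose of investigational product". The schedule has adverse events, vital signs, weight, chemistry, hematology, lipids and urinalysis collected at that visit.

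**The concern.** The SAP's parenthesis states a fact about the design, and the protocol's visit window contradicts it. The figure is also operative: it decides which off-drug observations are counted. A site that sees a patient 31 or 32 days after the last dose has followed the protocol, yet the measurements from that visit fall outside the analysis period for the categorical tables.

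Protocol 5.4 gives safety monitoring off drug as the purpose of Period 3, and Visit 801 is the visit scheduled for it. Data kept only in listings yield no incidence and no comparison with placebo. The patients who have this visit are those who do not enter the extension, including those who leave the study early after dosing.

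**Working it through.** **Inputs**

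| Quantity | Value | Source |
|---|---|---|
| Nominal day of Visit 801 | 28 days after last dose | Protocol 2 and 5.1.3 |
| Tolerance for Visit 801 | ±4 days | Protocol 2 |
| SAP cut-off | 30 days after last dose | SAP 6.14, 6.14.2, 6.14.3, 6.14.4 |

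**Step 1: try to reproduce the SAP's 30 days**

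- Nominal visit day: 28.
- Four-week follow-up period: 4 × 7 = 28.
- Total duration less screening and treatment: 25 − 5 − 16 = 4 weeks = 28 days.
- Nominal day plus the Visit 801 tolerance: 28 + 4 = 32.
- Nominal day plus a 2-day tolerance: 28 + 2 = 30.

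Only the last gives 30, and the schedule assigns ±2 days to Visits 3 to 5, not to Visit 801.

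**Step 2: planned maximum from the protocol**

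Latest compliant day = 28 + 4 = 32. Shortfall = 32 − 30 = 2 days.

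**Step 3: share of the visit window that is cut**

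The window runs from 28 − 4 = 24 to 32, which is 32 − 24 + 1 = 9 days. Days 31 and 32 lie outside the cut-off: 2/9 = 22% of the window's days.

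**Step 4: share of Visit 801 attendances (assumptions only)**

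The documents give no distribution of visit dates. If attendance were uniform over the 9 days, the share on days 31 and 32 would be 22%. If it were normal, centred on day 28 and truncated to the window, with each day taken as ±0.5, the share would be [Φ(4.5/SD) − Φ(2.5/SD)] / [2Φ(4.5/SD) − 1]:

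- SD 1.5 days: 4.7%
- SD 2 days: 9.6%
- SD 2.5 days: 13.2%

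These are shares of attendances at Visit 801, not of randomized patients and not of events.

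**Step 5: the TEAE clause**

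Take a patient whose last dose coincides with Visit 8, whose Visit 801 is 31 days later, and who has an adverse event starting on day 10 off drug.

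- By onset date, day 10 is within 30 days, so the event counts.
- By the clause on the last visit date, Visit 801 (day 31) is outside the analysis period, so the last visit inside it is Visit 8. Read literally, the event starts too late and is not a TEAE.

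With a 32-day period, Visit 801 on day 31 is inside and both readings agree. A visit later than day 32 would bring the disagreement back, so changing the constant alone does not remove the ambiguity.

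**The case against.** The strongest reply is that a fixed off-drug window is an analysis convention and need not equal a visit tolerance. The SAP applies 30 days consistently and anchors it to the last dose, not to a visit. On that view only the parenthetical label is wrong, and deleting it would restore consistency. Part of this stands: a fixed window is the right kind of rule. But the SAP does not call 30 days a convention. It calls it the planned maximum, and no reason is given for excluding on-schedule data. Deleting the label would leave the day 31 and 32 data out of the tables.

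A reader might infer that everything found at a late follow-up visit drops out, or that a patient's off-drug adverse events are lost. The documents do not support either as a general statement. SAP 6.14 includes data by when they occur, so an event that began by day 30 and was reported at a day 31 visit is inside the limit. It is lost only if the last-visit clause in 6.14.2 is read against 6.14 and against the clause's own 30 days of off-drug time. That is an ambiguity, not a settled loss.

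The cut is also not universal. Listings hold all safety data. Deaths are listed whenever they occurred during the study (6.14.2.2). Malignancy summaries ignore the time since last dose (6.14.5.10). Registry tables count serious events whether or not they are treatment-emergent (6.20).

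The laboratory effect is less certain than it looks. The treatment-emergent high/low definition in 6.14.3, and the hepatic, hematologic and renal summaries in 6.14.5, refer to the treatment period, while 6.14 and the opening of 6.14.3 add off-drug time. If those narrower definitions were followed literally, a longer window would not change those particular tables.

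**Conclusion.** The SAP is wrong as written: the protocol's planned maximum is 32 days after last dose, not 30. What the rule excludes from the event tables is limited to assessments dated day 31 or 32 at a compliant Visit 801 and adverse events that start on those days. The possible loss of earlier off-drug events depends on a literal reading of one clause and should be treated as a drafting ambiguity.

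The 5% to 22% range for attendances should not be read as a proportion of trial patients. It rests on assumed visit dates and applies only to those who attend Visit 801. Patients entering the extension do not need that visit, and the rationale given for the Section 10.2 change in Protocol Appendix 8 expects most patients to enter. The number affected cannot be derived from the documents and is probably small. The same rule applies in every arm, and the documents do not show a bias between arms. Efficacy analyses, alpha and power are not touched. The point is worth correcting because the contradiction is certain and the remedy is cheap, not because a large effect is shown.

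**What to change.** 1. Replace 30 with 32 days after last dose in SAP 6.14 (both uses), 6.14.2, 6.14.3 and 6.14.4. The planned-maximum label is then correct.
2. In the TEAE definition in 6.14.2, make the upper bound the end of the analysis period in place of the last visit date within it.
3. Keep the window fixed, and do not define it as running to Visit 801. Extension patients have no such visit. Patients off drug for more than 28 days may combine it with Visit 8/early termination (Protocol 2, footnote a) or need no separate one (Protocol 5.1.3). A visit-based end would give unequal and possibly much longer off-drug windows.

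The cost is SAP wording and one programming constant. Where incidence rates are given, observation time for patients without the event runs to the end of the analysis period (6.14.2), so those denominators must use the same constant. Trial conduct and data collection do not change.

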6.14.1. Extent of Exposure

Duration of exposure (in days) will be calculated as follows:

- Duration of exposure to investigational product (including exposure after the initiation of rescue therapy): *date of last dose of study drug including rescue – date of first dose of study drug + 1.*

Last dose of study drug including rescue is calculated as last date on study drug. For patients discontinuing study drug or study due to the reason ‘Lost to Follow-up’, the duration of exposure is calculated as *date of to second last visit - date of first dose of study drug + 1.*

Total patient-years (PY) of exposure to study drug will be reported for each treatment group for overall duration of exposure. Descriptive statistics will be provided for patient-days of exposure and the frequency of patients falling into different exposure ranges in addition to cumulative exposures will be summarized.

Exposure ranges will be summarized as follows:

- ≥ 28 days, ≥ 56 days, ≥ 84 days, and ≥ 112 days
- >0 to <28 days, ≥ 28 days to <56 days, ≥ 56 days to <84 days, ≥ 84 days to <112 days, and ≥ 112 days

Overall exposure for a treatment group will be summarized in total PY which is calculated according to the following formula:

- $Exposure\ in\ PYE = sum\ of\ duration\ of\ exposure\ in\ days\ / 365.25$

